6.4.2 Determination of Drug Concentrations in Blood Samples

Determination of ASLAN003 and LAS186558 plasma concentrations by using a validated liquid chromatography/mass spectrometry methodology will be performed by a sponsor designated bioanalytical laboratory.

The analytical methods used to measure plasma concentrations of study drug will be described in a separate bioanalytical report.

The following information will be captured for blood sample collections in each patient's eCRF:

1. Patient's number and initial.
2. Date/time of the drug administration.
3. Time and date of each blood sample collected for PK analysis

6.5 Other Exploratory Assessment

Assays including but not limited to *ex vivo* flow cytometry assay using selected myeloid cell markers (such as CD11b) will be performed to assess the degree of blast cell differentiation upon treatment with ASLAN003. The percentage of CD11b positive cells will be determined before and after *ex vivo* treatment with ASLAN003. Molecular abnormalities of AML patients will be assessed using polymerase chain reaction (PCR) or next-generation sequencing (NGS). The *ex vivo* assay and molecular assessment will be processed centrally (Please refer to the lab manual for details).

6.6 Demographics and Baseline Characteristics

Demographics and baseline characteristics consist of those variables that are assessed only at Screening.

6.6.1 Patient Demography

Patient demography consists of:

- Date of birth;
- Height;
- Weight;
- Vital signs;
- Race and ethnicity;
- Gender.

Demographic information will be recorded in the eCRF

6.6.2 Disease History

For disease history the following information related to AML will be documented:

- Date of first diagnosis
- Diagnosis as per World Health Organization 2016 revised classification;
- Prior treatment, response and date;

- Date of relapse / failed response to previous therapy;

6.6.3 Medical History

For the documentation of the medical history, any relevant previous and concurrent diseases will be documented.

The medical history will be obtained by interviewing the patient or by inspecting his/her medical records. Findings will be recorded in the eCRF.

For coding of medical history, see Section 9.4

6.6.4 Previous and Concomitant Medications

Previous and concomitant medication will be documented as described in Section 5.8.

6.7 Other Variables

Not applicable.

7 STUDY CONDUCT

7.1 Schedule of Procedures

The timing and details of study procedures to be conducted, by visit, is described in Table 1.

7.2 Procedures by Visit

7.2.1 Screening (Days -28 to 0)

Prior to any study activities, patients will be asked to read and sign an ICF that has been approved by an IEC/IRB and the Sponsor and which complies with regulatory requirements.

Patients will undergo Screening during a visit that can occur up to 4 weeks prior to the Cycle 1 Day 1 Visit. This Screening period will be used to assess eligibility of patients and to allow for the washout of prohibited medications.

The following Screening and baseline assessments will be performed:

- Obtain written informed consent;
- Verify conformance with entry criteria;
- Assignment of a Screening number;
- Demographic data;
- Other medical history/prior medications;
- Complete physical examination;
- Height;
- Body weight;
- Vital signs (blood pressure, heart rate, respiratory rate, and body temperature);
- 12-lead ECGs;
- Patients' ECOG performance status;
- Prior and Concomitant Medications;
- Routine laboratory evaluations (chemistry, hematology, liver function test and urinalysis);
- Serum / urine β -human Chorionic Gonadotropin
- Serology;
- Coagulation laboratory test;
- Bone Marrow Aspiration (BMA) [*BMA smears will be processed locally. Remaining Bone Marrow Aspiration Sample will be processed as per BMA lab manual for ex vivo assay and molecular assessment*].

7.2.2 Treatment Visits

Patients will receive study drug ASLAN003 from Day 1 in 28-day treatment cycles until disease relapse, treatment failure, unacceptable toxicity, and withdrawal of consent or death.

Treatment visits are scheduled as below:

Visit 1: Cycle 1, Day 1

Visit 2: Cycle 1, Day 8

Visit 3: Cycle 1 Day 10

Visit 4: Cycle 1, Day 15

Visit 5: Cycle 1, Day 22

Visit 6 & onwards: Cycle 2, Day 1 and onwards at Day 1 of every subsequent cycle.

7.2.2.1 Cycle 1, Day 1

The following procedures will be conducted at this visit:

- Complete physical examination;
- Body weight;
- Vital signs (blood pressure, heart rate, respiratory rate, body temperature);
- Patients' ECOG performance status;
- All AEs since the last visit will be recorded;
- Concomitant medications will be recorded;
- Routine laboratory evaluations (chemistry, hematology, liver function test and urinalysis);
- Study drug (ASLAN003) will be dispensed and administered.
- Blood sample will be collected for PK analysis at Day 1, QD regime: pre-dose, 1, 2, 4, 5, 6, 8, and 24 hours post dose In BID regime i.e 100mg BID and 200mg BID the PK sampling will be done at following timepoints: pre-dose, 1, 2, 4, 5, 6, 8, and 12 hours (or evening pre-dose). For Part 2- Steering Committee will decide whether PK analysis is required or not and ASLAN pharmaceuticals will be updated accordingly.

7.2.2.2 Cycle 1, Day 8 (± 1 day)

The following procedures will be conducted at this visit:

- Complete physical examination;
- Vital signs (blood pressure, heart rate, respiratory rate, body temperature);
- All AEs since the last visit will be recorded;
- Concomitant medications will be recorded;
- Routine laboratory evaluations (chemistry, hematology, liver function test and urinalysis);
- Study drug (ASLAN003) will be dispensed and administered.

- Blood sample will be collected for PK analysis at Day 8, QD regime: pre-dose, 1, 2, 4, 5, 6, 8, and 24 hours post dose. In BID regime i.e 100mg BID and 200mg BID the PK sampling will be done at following timepoints: pre-dose, 1, 2, 4, 5, 6, 8, and 12 hours (or evening pre-dose). For Part 2- Steering Committee will decide whether PK analysis is required or not and ASLAN pharmaceuticals will be updated accordingly.

7.2.2.3 Cycle 1, Day 10 (+1 day)

The following procedures will be conducted at this visit:

- AST, ALT and total bilirubin to be performed;
- Study drug (ASLAN003) will be dispensed and administered.

7.2.2.4 Cycle 1, Day 15 (± 2 days)

The following procedures will be conducted at this visit:

- Complete physical examination;
- Vital signs (blood pressure, heart rate, respiratory rate, body temperature);
- 12-lead ECG
- All AEs since the last visit will be recorded;
- Concomitant medications will be recorded;
- Routine laboratory evaluations (chemistry, hematology, liver function test and urinalysis);
- Coagulation laboratory test;
- Study drug (ASLAN003) will be dispensed and administered.

7.2.2.5 Cycle 1, Day 22 (± 2 days)

The following procedures will be conducted at this visit:

- Complete physical examination;
- Vital signs (blood pressure, heart rate, respiratory rate, body temperature);
- All AEs since the last visit will be recorded;
- Concomitant medications will be recorded;
- Routine laboratory evaluations (chemistry, hematology, liver function test and urinalysis);
- Study drug (ASLAN003) will be dispensed and administered.

7.2.2.6 Cycle 2 and Subsequent Cycles - Day 1 (± 2 days)

On Day 1 of Cycle 2 and all subsequent cycles, the following procedures will be conducted:

- Complete physical examination;
- Body weight;
- Vital signs (blood pressure, heart rate, respiratory rate, body temperature);
- 12-lead ECG (only on Cycle 2 Day 1);
- All AEs since the last visit will be recorded;

- Concomitant medications will be recorded;
- Routine laboratory evaluations (chemistry, hematology, liver function test and urinalysis);
- Study drug (ASLAN003) will be dispensed and administered.
- BM aspiration is mandatory to be performed on Day 1 of every cycle from Cycle 2 to Cycle 5 and every 3 months thereafter. Patients achieving CR could omit the bone marrow aspiration at a subsequent assessment if there is a normal complete blood count with differential of peripheral blood. Investigator may perform additional BM aspirate if required based on clinical judgment. BM aspiration smear will be processed locally.

7.2.3 End of Treatment (EOT) Visit

Patients who discontinue from the study drug should have an EOT visit. This visit should take place as soon as possible within 7 days of last dose of study treatment after the patient stops taking study drug. At this visit, the following procedures will be conducted:

- Complete physical examination;
- Body weight;
- Vital signs (blood pressure, heart rate, respiratory rate, body temperature);
- 12-lead ECG
- Patients' ECOG performance status;
- All AEs since the last visit will be recorded;
- Concomitant medications will be recorded;
- Routine laboratory evaluations (chemistry, hematology, liver function test and urinalysis);
- Serum / urine β -human Chorionic Gonadotropin;
- Coagulation laboratory test.

7.2.4 Safety Follow-up (± 7 days)

Patient will complete a safety follow-up visit 28 days after the last dose of ASLAN003. The following procedures will be performed:

- Complete physical examination;
- 12-lead ECG
- Vital signs (blood pressure, heart rate, respiratory rate, body temperature);
- All AEs since the last visit will be recorded;
- Concomitant medications will be recorded.

7.2.5 Survival Follow-up (± 7 days)

Survival follow-up by either telephone or clinic visit will be performed in patients achieving CR or CRi every 12 weeks post EOT until disease relapse or death (in the absence of disease relapse) to enable the assessment of RFS.

8 STATISTICAL METHODS

All statistical analyses will be performed by or under the direct auspices of ASLAN Pharmaceuticals, using SAS® version 9.3 or higher. Further details will be provided in the Statistical Analysis Plan (SAP).

8.1 General Statistical Considerations

There are no formal statistical analyses planned. All primary and secondary endpoints will be listed and summarized using appropriate descriptive statistics.

8.2 Sample size determination

This Phase IIA study is not formally powered. For Part 1, the proposed design of up to 6 patients per dose cohort has been selected to provide an assessment of the safety, tolerability and efficacy of up to 4 dose cohorts of ASLAN003, in order to select the most appropriate dose for further exploration in Part 2.

Part 2 is not formally powered. The sample size of 20 patients has been selected to provide further efficacy and tolerability data at the selected dose level from Part 1, prior to conducting larger randomized trials in AML.

8.3 Analysis population

8.3.1 Safety Population

The safety population will include all patients who received at least 1 dose drug in the study. Patients will be included in the safety population according to the dose initially received, regardless of any subsequent dose modifications.

The safety set will be the primary analysis set used for the assessment of safety and tolerability in the study

8.3.2 Full Analysis Set

The full analysis set (FAS) is defined as the set of patients who received at least 1 dose of study drug, regardless of any protocol deviations or dosing errors. Patients will be included in the FAS according to the intended initial dose cohort, regardless of any subsequent dose reductions, increases or interruptions.

The FAS will be used to assess the sensitivity of the primary efficacy analyses (based on the evaluable for response [EFR]) to exclusions from the EFR.

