3 OVERALL DESIGN AND PLAN OF THE STUDY

3.1 Study Design Overview

This is a multicenter, single arm, non-randomized, Phase IIA Study to evaluate ASLAN003 as a monotherapy in patients with AML.

AML patients who are ineligible for standard treatment including, but not limited to the following conditions, will be enrolled in the study:

- Newly diagnosed patients who are ineligible for standard therapy i.e., standard dose induction chemotherapy and reduced dose chemotherapy;
- Patients with relapse from prior remission;
- Patients with failed response to prior therapy including chemotherapy, hypomethylating agents, and bone marrow transplantation.

Rationale for dose selection: ASLAN003 is very potent at inducing differentiation in AML cells lines ($ED_{90} < 50$ nM for THP-1). From these predictions, a starting dose of 100 mg QD would be the most appropriate to obtain a good coverage of ED_{90} values. Since ASLAN003 is an acidic compound, the protein binding effect in human plasma will be high leading to lower levels of free drug, a starting dose of 100 mg QD is recommended to provide full 24-hour coverage.

Blast cell counts vary widely among AML patients, which may indicate that a higher treatment dose of ASLAN003 might be necessary to obtain the optimum efficacy. However, it is also important to consider the age and fitness of the AML patients who might have multiple comorbidities, and the maximum experienced dose (400 mg QD) established in healthy subjects might not be tolerated. Considering that AML patients are generally older in age and often carry comorbidities, it may be prudent to use doses lower than the maximum dose (400 mg) determined in healthy subjects.

Up to a total of 18-24 patients will be enrolled in Part 1 of this study - 6 patients in each dose cohort. The planned sequence of cohort enrollment is ASLAN003 100 mg QD, 200 mg QD, 100 mg BID and potentially an additional cohort of 200 mg BID (this additional cohort of 6 patients may commence, subject to agreement by the steering committee (SC) based on a review of safety data in 100 mg BID cohort).

A SC meeting will be set up to review all the clinical information including efficacy, safety, and PK data. Details of the SC outcome will be specified in the SC charter.

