3.4 Duration of the study participation

The study duration consists of the following periods:

Screening Period: 28 days

Treatment Period: All patients will receive a continuous 28-day treatment cycle of ASLAN003 until disease relapse, treatment failure (defined as failure to achieve a PR or higher within 4 cycles) unacceptable toxicity, withdrawal of consent or death.

Follow-up Period: All patients will be required to complete a safety follow-up visit within 28 days after the last dose of study treatment. All patients achieving CR or CRi will be followed for survival every 12 weeks post end of treatment (EOT) until disease relapse or death (in the absence of disease relapse) to find out the RFS.

Visit Schedule: In order to address the primary objectives of the study, if treatment is interrupted for any reason, it is important that all planned safety and efficacy assessments are performed at the scheduled time, regardless of whether the patient is receiving study treatment, or not, at the time.

The planned duration of entire study (treatment and follow-up) is approximately 2 years.

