4.3 Patient Withdrawal and Replacement

Patients may withdraw from any part of the study at any time without penalty and for any reason without prejudice to his or her future medical care. The Investigator will advise the Sponsor of the withdrawal of any patient.

Patients must be withdrawn from study drug under the following circumstances:

- Patient voluntarily withdraws from study participation;
- Disease recurrence;
- Ineffective treatment;
- Unacceptable toxicity;
- Patient's withdrawal of consent;
- Death;
- Pregnancy (refer to section 6.3.1.11)
- Significant protocol deviation;
- Lost to follow-up;
- If deemed by the Investigator that it is not in the patient's interest to continue with the study.

Withdraws from study participation (follow-up permitted):

Patients withdrawing from the study drug will be encouraged where possible to return to the site for a study follow-up visit, in particular for safety evaluations, study assessments and survival follow-up.

Disease recurrence:

Sites should continue to perform efficacy assessments for patients achieving CR or CRi until disease recurrence (or death in the absence of recurrence) in accordance with IWG criteria for AML. Patients will be withdrawn from the treatment if there is evidence of disease recurrence as defined by IWG Criteria¹⁶ (Cheson, 2003).

Ineffective treatment:

The study drug may be discontinued in the event of:

- Treatment failure (in patients who do not achieve a PR or above after 4 cycles of treatment)
- Relapse, as defined by the IWG Response criteria (for patients with a CR or CRi)
- No longer meeting the criteria for a PR (in patients who were previously determined to have a PR)

Once ineffective treatment has been established, as described above, no further efficacy assessments are required.

Unacceptable toxicity:

If the symptoms are not controlled with standard treatments and are considered to be clinically significant, study drug will be stopped and the patient will be withdrawn from the study drug. Patients removed from study drug for unacceptable toxicity will be followed until resolution or stabilization of the AE.

Patients with a response (CR or CRi) withdrawn from the treatment prior to disease relapse should continue to be followed until the relapse in accordance with the study plan.

Consent Withdrawal:

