5.4 Intra-patient dose escalation

Intra-patient dose escalation is allowed when the patient has no ongoing study drug-related AE, and all patients in the cohort of targeted dose have completed at least one cycle of treatment without unexpected safety issue identified. Prior agreement with ASLAN Pharmaceuticals would need to be obtained for the dose escalation.

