Failure to meet the criteria for CR, CRi or PR after 4 cycles of treatment will result in a best response of treatment failure.

For the evaluation of OCRR, a binary variable will be created to indicate complete response status of each patient (complete responder or non-responder) defined as follows:

A patient will be classified as a complete responder if either of the following are achieved during the study:

- Achievement of CR
- Achievement of CRi

Patients who do not satisfy the CR criteria outlined above (including patients with PR, treatment failure and any patients without evaluable post-treatment assessments) will be classified as non-responders for the assessment of OCRR.

Best response status will also be assessed. A patient's best response is defined as the best AML visit response observed, ranked in the following order:

CR > CRi > PR > Treatment failure.

Based on the above definitions, the following efficacy endpoints will be evaluated:

Overall Complete Remission Rate: Defined as the proportion of patients with a best response of CR or CRi, defined in accordance with the IWG Response Criteria in AML, and described above.

Relapse Free Survival: Defined as the time the criteria for remission (CR or CRi) are first met until there is evidence of patient relapse or death from any cause (whichever happens first), regardless of whether the patient is still taking study drug.

Relapse is defined as:

- The reappearance of leukemic blasts in the peripheral blood or > 5% blasts in the BM not attributable to any other cause
- The appearance of new dysplastic changes
- The reappearance of or development of cytologically proven extramedullary disease
- The reappearance of a cytogenetic or molecular abnormality

Clinical Benefit Rate: Defined as the proportion of patients with an AML IWG best response of CR, CRi or PR.

The percentage change from baseline in BM blasts and peripheral blood blasts at Day 29 will also be evaluated.

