2.1 Overall Study Design

This study is designed as a multicenter, single arm, non-randomized phase IIA study to evaluate ASLAN003 as a monotherapy in patients with AML.

AML patients who are ineligible for standard treatment including, but not limited to the following conditions, will be enrolled in the study:

- Newly diagnosed patients who are ineligible for standard therapy i.e., standard dose induction chemotherapy and reduced dose chemotherapy
- Patients with relapse from prior remission
- Patients with failed response to prior therapy including chemotherapy, hypomethylating agents, and bone marrow transplantation.

[figure not shown]
Part 1:

Up to a total of 24 patients will be enrolled into Part 1 of this study – 6 patients in each dose cohort (ASLAN003 100 mg once daily (QD), 200 mg QD, 100 mg twice daily (BID) and 200 mg BID, respectively). Once 6 patients have been enrolled into the cohort of 100 mg QD, recruitment will be started in the cohort of 200 mg QD. The same rule applies to the 100 mg BID and 200 mg BID cohorts. A steering committee (SC) meeting will be set up and meet to review all safety data. Details of the SC outcome will be specified in the SC charter.

Part 2:

An expansion cohort of 20 patients will be recruited to study the optimum dose selected by the SC. The optimum dose will be selected from at least one cohort showing tolerable safety profile and clinical benefit in disease presentation. Details will be specified in the SC charter.

Figure 1: Study Design

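### After a permitted dose escalation, SAP 3.2.2 leaves the intended dose unadjusted in PID and undefined in RDI, and no Part 1 summary separates post-escalation data (minor)

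*Protocol*

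**What the plan says.** **Escalation.** Protocol 5.4 states: "Intra-patient dose escalation is allowed when the patient has no ongoing study drug-related AE". It adds that "all patients in the cohort of targeted dose have completed at least one cycle of treatment without unexpected safety issue identified", and the sponsor must agree beforehand. Cohorts open in sequence; SAP 2.1 says "Once 6 patients have been enrolled into the cohort of 100 mg QD, recruitment will be started in the cohort of 200 mg QD" and applies the same rule to the two BID cohorts.

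**Dose intensity.** SAP 3.2.2 defines PID and RDI, each as 100% × d/D.
- In PID, d is the total dose actually taken. D is the total that would have been given had dose and schedule stayed as first planned.
- In RDI, D is only called the intended cumulative dose, with no statement of what is intended after an escalation.
- The section's introduction mentions interruptions and reductions, not increases.
- Dosing counts to relapse for patients with CR or CRi, and to the end of cycle 4 for everyone else.
- The same section defines actual exposure, which removes every day on which no drug was taken, whatever the reason.

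**Attribution.** Protocol 8.3.2 says of the full analysis set: "Patients will be included in the FAS according to the intended initial dose cohort, regardless of any subsequent dose reductions, increases or interruptions". The evaluable-for-response set, primary for efficacy, is a subset of it. The safety population (Protocol 8.3.1, SAP 4.1) uses the dose first received. Part 1 best response, OCRR, CBR, best bone marrow blast change and TEAEs are then shown by that dose (SAP 7.1, 7.3, 7.4, 7.7.1). SAP 3.1.1 uses efficacy data until subsequent AML therapy starts. No table in SAP 9.1 stops at escalation or is split by it.

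**The concern.** Protocol 3.3.1 makes exposure and dose intensity part of the Part 1 primary safety and tolerability endpoint. When a patient escalates, PID's numerator rises and its denominator does not. The ratio then mixes two things, a higher prescription and adherence to it, and a shortfall in the second can be offset by the first. A reader who takes a value near 100% as good tolerability could be wrong about exactly the patients on the higher dose.

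The secondary point concerns reading dose-response, which Protocol 6.1 gives as the purpose of the Part 1 review. For an escalated patient, a later response or a later adverse event is tabulated under a dose the patient had already left. With six patients per cohort, one such patient is visible in the rate.

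**Working it through.** **Inputs.** Cohort size is 6 (Protocol 3.1); 3 × 6 = 18 and 4 × 6 = 24 reproduce the stated Part 1 total. The failure window is 4 cycles of 28 days = 112 days (Protocol 3.4). The plan gives no worked PID. The escalation days and missed fractions below are assumptions for illustration.

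**1. PID as written.** Let f be the share of the counted period after escalation, k the ratio of new to old daily dose, and m the share of escalated doses missed. Then PID = 1 + f × [k(1 − m) − 1]. For a doubling (k = 2) this is 1 + f(1 − 2m). It exceeds 100% whenever less than half of the escalated doses are missed, and equals 100% at m = 0.5 for any f.

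*Example A:* 100 to 200 mg QD after day 70 of 112, so f = 42/112 = 0.375.
- D = 112 × 100 = 11,200 mg. Prescribed = 70 × 100 + 42 × 200 = 15,400 mg.
- None missed: 15,400/11,200 = 137.5%.
- A quarter missed: 13,300/11,200 = 118.8%, against 13,300/15,400 = 86.4% of prescribed.
- Half missed: 11,200/11,200 = 100.0%, against 11,200/15,400 = 72.7% of prescribed.

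*Example B:* a CR/CRi patient counted for 336 days, 100 to 200 mg QD after day 168, half of the escalated doses missed.
- Taken = 16,800 + 16,800 = 33,600 mg; D = 33,600 mg; PID = 100.0%.
- Prescribed = 16,800 + 33,600 = 50,400 mg, so 66.7% of prescribed.

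*Example C:* 100 mg BID to 200 mg BID after day 70 of 112, one of the two daily doses missed every day thereafter.
- Taken = 70 × 200 + 42 × 200 = 22,400 mg; D = 112 × 200 = 22,400 mg; PID = 100.0%.
- Prescribed = 70 × 200 + 42 × 400 = 30,800 mg, so 72.7% of prescribed.

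**2. Does actual exposure reveal it?** Yes in A (half missed) and B, where whole days are lost: (112 − 21)/112 = 91/112 = 81.3%, and (336 − 84)/336 = 252/336 = 75.0%. No in C: drug is taken on every day, so actual exposure is 112/112 = 100%.

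**3. Where PID is affected.** For PR and treatment-failure patients, dosing after cycle 4 is ignored. The defect therefore applies to escalation within 4 cycles, or to patients with CR/CRi. A move from 200 mg QD to 100 mg BID leaves the daily total at 200 mg and does not affect PID.

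**4. Which responses are exposed.** The whole target cohort must finish a cycle first, so Part 1 first-cycle events and Day 29 blasts are essentially pre-escalation. For patients without a response, Protocol 6.2 says "Failure to meet the criteria for CR, CRi or PR after 4 cycles of treatment will result in a best response of treatment failure". Protocol 4.3 is permissive ("The study drug may be discontinued in the event of"), and SAP 3.1.1 does not say whether its all-data rule overrides the 4-cycle classification. The clear late route is a patient in PR who escalates and then reaches CR or CRi. That response counts for the starting cohort: 1/6 = 16.7 points of OCRR.

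**5. How many could escalate within 4 cycles (illustration only).** Assume one patient every r days and no gap between cohorts. When the next cohort has finished cycle 1, patient k of the lower cohort has been on drug (12 − k)r + 28 days. The number below 112 days is 3 of 6 at r = 10 and 0 at r = 14. A 14-day gap between cohorts cuts the count at r = 10 from 3 to 1. Moving two cohorts up gives 0 of 6 at r = 7 or slower. Protocol 3.4 says "The planned duration of entire study (treatment and follow-up) is approximately 2 years". With 38 to 44 patients, that fits r of 13.7 to 15.9 days if 140 days are kept for the last patient (0 to 1 of 6), or 8.5 to 9.9 days if 365 are kept (3 to 4 of 6). The documents do not settle the number.

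**The case against.** **Starting-dose attribution is standard and was chosen knowingly**, since Protocol 8.3.2 names increases. This stands. It should remain the main analysis.

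**Missed doses are visible elsewhere.** Actual exposure has its own summary (Table 14.3.1.1), given by cycle for cycles 1 to 3 and overall. Protocol 5.8 has missed-dose dates recorded, and drug administration and compliance are listed (16.2.5.1, 16.2.5.4). This stands for whole missed days, so a reader who inferred that missed doses vanish from the report would be wrong. It does not cover single missed BID doses in the summaries, and it does not make PID itself interpretable. A PID of exactly 100% is a special case, but values above 100% despite missed doses are not.

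**Patient-level tracing exists.** AE listings carry dose at onset, and the swimmer plot is repeated to account for dose modifications (SAP 7.7.1). With six per cohort and no formal analysis, listings are usable. This largely stands, and it is why the point is minor. Listings do not give rates, denominators or patient-time at each dose.

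**A stronger inference is tempting:** that the wrong dose would be carried into Part 2. The documents do not support it. Protocol 3.1 says "A SC meeting will be set up to review all the clinical information including efficacy, safety, and PK data", and the charter governing the choice is not among these documents. The one numerical committee rule found, on halting recruitment (Protocol 6.3.1.6, Note 2), uses first-cycle events. Any probability that cohorts are ranked in the wrong order would need response rates, accrual and escalation counts that the documents do not give.

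**Conclusion.** The PID point holds on the text alone. For a dose change the protocol permits, the stated formula can exceed 100% or mask missed escalated doses: 137.5% with full adherence, and 100.0% when 72.7% of the prescribed amount was taken, under the assumed day-70 doubling. For RDI the intended dose after escalation is undefined, which is a gap and not a demonstrated error.

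The secondary point holds as an omission: no planned Part 1 summary separates post-escalation data, and one late response moves a cohort's OCRR by 16.7 points. It is not a finding that the starting-dose tables are wrong or that dose selection is biased. Whether anyone escalates, how many, and with what effect on the dose chosen cannot be determined from the documents. Severity is minor.

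**What to change.** 1. **SAP 3.2.2.** State that from the date of an agreed escalation, D in both PID and RDI is the prescribed escalated dose. Reductions and interruptions remain shortfalls, as now. Example A then reads 100% with full adherence and 72.7% with half of the escalated doses missed.
2. **SAP 7.1, 7.3 and 7.4.** Keep the initial-dose displays as the main ones. If any patient escalates, add supplementary Part 1 by-cohort summaries of best response, OCRR, CBR and best blast change that use only assessments before the first dose increase. Define *increase* before data review, because 200 mg QD and 100 mg BID share a daily total.
3. **SAP 7.7.1.** If any patient escalates, add a Part 1 TEAE table by dose at onset, with patients and patient-time at each dose.
4. **Listing 16.2.6.4.3.** If any patient escalates, show the dose at first response.

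The cost is SAP wording and a few extra outputs from data already collected (dosing dates, response dates, dose at onset). The downside is that the truncated response summaries shorten follow-up in a selected group, so they are read beside the main tables and not in place of them. If nobody escalates, items 2 to 4 can be omitted.
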